5.5.4 Treatment Interruption for Interstitial Lung Disease

In the event of acute onset (grade \geq 2) or worsening pulmonary symptoms which are not thought to be related to underlying cancer, both cetuximab and ficlatuzumab should be interrupted and a prompt investigation of these symptoms should occur. Neither ficlatuzumab nor cetuximab retreatment should occur until these symptoms have resolved to grade 1. If interstitial lung disease is confirmed, both cetuximab and ficlatuzumab should be discontinued permanently and the patient should be treated appropriately.

5.5.5 Dose Modification for Hematologic Toxicity

While serious (Grade 3-4) myelosuppression has not been observed with ficlatuzumab monotherapy or the combination of ficlatuzumab with EGFR-inhibitors during phase I development, dose modifications are specified in Table 4A for neutropenia or thrombocytopenia, should either be observed during the course of this phase II study. As cetuximab does not cause myelosuppression, the cetuximab dose will not be affected by observed neutropenia or thrombocytopenia.

Table 4A. Ficlatuzumab and Cetuximab Dose Modifications for Hematologic Toxicity

| Adverse Event NCI CTCAE Toxicity Grade (CTCAE v. 4.0) | Ficlatuzumab Dose | Cetuximab Dose |
|---|---|---------------------|
| Neutropenia | | |
| Grade 1-2 1 (1,500-1,999/mm³) 2 (1,000-1,499/mm³) | Maintain dose level | Maintain dose level |
| Grade ≥3: 3 (500-999/mm³) 4 (<500/mm³) | Hold dose. When recovered to Grade 2 or | Maintain dose level |

| | better, decrease by 1 dose level. | |
|---|---|---------------------|
| Thrombocytopenia | | |
| Grade 1 (75,000/mm ³ -LLN) | Maintain dose level | Maintain dose level |
| Grade ≥ 2: 2 (50,000-74,999/mm³) 3 (25,000-49,999/mm³) 4 (<25,000/mm³) | Hold dose. Re-assess prior to next scheduled dose. When recovered to Grade 1 or better, decrease by 1 dose level. | Maintain dose level |

5.5.6 Dose Modification for Non-Hematologic Toxicity

Adverse events observed and deemed to be at least possibly related to study drug(s) will be managed according to the guidelines for dose interruption, delay, or reduction.

If the non-hematologic toxicity can be clearly and solely attributed to ficlatuzumab, the ficlatuzumab should be withheld or reduced as described below in Table 4B. If the non-hematologic toxicity is at least possibly related to both ficlatuzumab and cetuximab, then both study drugs should be modified as described below. If the non-hematologic toxicity can be clearly and solely attributed to cetuximab, the cetuximab should be withheld or reduced as described below in Table 4B.

Table 4B. Ficlatuzumab and Cetuximab Dose Reductions for Non-Hematologic Toxicity

| Adverse Event NCI CTCAE Toxicity Grade (CTCAE v. 4.0) | Ficlatuzumab Dose | Cetuximab Dose |
|---|---|---|
| Metabolic ^a Hypomagnesemia, Hypokalemia, Hypophosphatemia, or Hyponatremia | | |
| Grade ≥ 3, Asymptomatic | Administer PO or IV replacement and reassess. If Grade ≤2, continue drug at same dose level. (Same day re-assessment and dosing is permissible.) If AE does not recover to Grade ≤2, hold drug. | Administer PO or IV replacement and reassess. If Grade ≤2, continue drug at same dose level. (Same day re-assessment and dosing is permissible.) If AE does not recover to Grade ≤2, hold drug. |
| Grade ≥ 3, Symptomatic | Administer PO or IV replacement and reassess. If | Administer PO or IV replacement and reassess. If |

| Adverse Event | Ficlatuzumab Dose | Cetuximab Dose |
|---|--|--|
| NCI CTCAE Toxicity Grade | Ficiatuzumab Dose | Cetuximab Dose |
| (CTCAE v. 4.0) | | |
| , | ≤ Grade 2 and asymptomatic, | ≤ Grade 2 and |
| | then reduce by one dose | asymptomatic, then reduce |
| | level. (Same day re- | by one dose level. (Same day re-assessment and dosing is |
| | assessment and dosing is permissible.) If AE does not | permissible.) If AE does not |
| | recover to Grade ≤2 and | recover to Grade ≤2 and |
| | asymptomatic, hold drug. | asymptomatic, hold drug. |
| Hepatic Function | | |
| AST and/or ALT Elevation | | |
| Grade 2 | Reduce by one dose level | Reduce by one dose level |
| Grade ≥ 3 | Hold drug until ≤ grade 2 | Hold drug until ≤ grade 2 |
| 6.446 = 5 | then reduce by one dose level | then reduce by one dose level |
| AST or ALT elevation >3x ULN and concomitant elevation of bilirubin >2x ULN | Discontinue ficlatuzumab | Discontinue cetuximab |
| Low Albumin | | |
| Grade 3 | No dose reduction | No dose reduction |
| Grade 4 | Reduce by one dose level | No dose reduction |
| Edema: Head/Facial/Neck edema and peripheral edema are to be managed individually. | | |
| Head/Facial/Neck Edema | | |
| Tolerable Grade ≤ 2 | No dose reduction. Treat with PO diuretics as clinically indicated. | No dose reduction |
| | Hold drug. Administer steroids ^c and/or PO or IV | No dose reduction |

| Adverse Event NCI CTCAE Toxicity Grade (CTCAE v. 4.0) | Ficlatuzumab Dose | Cetuximab Dose |
|---|--|---|
| Intolerable b Grade 2 (per opinion of treating investigator) or Grade ≥ 3 | diuretics as clinically indicated. Resume drug when ≤ tolerable grade 2 and reduce by one dose level. | |
| Peripheral Edema Tolerable Grade ≤ 2 | No dose reduction. Treat with PO diuretics as clinically indicated. | No dose reduction |
| Intolerable b Grade 2 (per the opinion of treating investigator) or Grade ≥ 3 | Hold drug. Administer steroids of and/or PO or IV diuretics as clinically indicated. Resume drug when ≤ tolerable grade 2 and reduce by one dose level. | No dose reduction |
| Fatigue | | |
| Grade ≥ 3, lasting more than 7 days | Hold drug until ≤ grade 2 then reduce by one dose level | Hold drug until ≤ grade 2 then reduce by one dose level |
| Nausea/Vomiting | | |
| ≥ Grade 3 with maximal medical management | Hold drug until ≤ grade 2 then reduce by one dose level | Hold drug until ≤ grade 2 then reduce by one dose level |
| Dermatologic events | | |

| Adverse Event NCI CTCAE Toxicity Grade (CTCAE v. 4.0) | Ficlatuzumab Dose | Cetuximab Dose |
|---|---------------------|--|
| Rash, Acneiform (Grade per Table 5 below.) | | |
| ≥ Grade 3 | Maintain dose level | First Occurrence: Hold drug for two weeks. If improved to ≤ grade 2 then restart cetuximab at same dose level. If rash remains ≥ Grade 3 then discontinue cetuximab. |
| | | Second Occurrence: Hold drug for two weeks. If improved to ≤ grade 2 then restart cetuximab at dose level -1. If rash remains ≥ Grade 3 then discontinue cetuximab. |
| | | Third Occurrence: Hold drug for two weeks. If improved to ≤ grade 2 then restart cetuximab at dose level -2. If rash remains ≥ Grade 3 then discontinue cetuximab. |
| | | Fourth occurrence: discontinue cetuximab. |

| Adverse Event NCI CTCAE Toxicity Grade (CTCAE v. 4.0) | Ficlatuzumab Dose | Cetuximab Dose |
|---|---------------------|---|
| Paronychia (Grade per Table 5 below.) | | |
| ≥ Grade 3 | Maintain dose level | First Occurrence: Hold drug for two weeks. If improved to ≤ grade 2 then restart cetuximab at same dose level. If paronychia remains ≥ Grade 3 then discontinue cetuximab. |
| | | Second Occurrence: Hold drug for two weeks. If improved to ≤ grade 2 then restart cetuximab at dose level -1. If paronychia remains ≥ Grade 3 then discontinue cetuximab. |
| | | Third Occurrence: Hold drug for two weeks. If improved to ≤ grade 2 then restart cetuximab at dose level -2. If paronychia remains ≥ Grade 3 then discontinue cetuximab. |
| | | Fourth occurrence: discontinue cetuximab. |
| Pruritus (Grade per Table 5 below.) | | |
| ≥ Grade 3 | Maintain dose level | First Occurrence: Hold drug for two weeks. If improved to ≤ grade 2 then restart cetuximab at same dose level. If pruritus remains ≥ Grade 3 then discontinue cetuximab. |

| Adverse Event | Ficlatuzumab Dose | Cetuximab Dose |
|--|---------------------|---|
| NCI CTCAE Toxicity Grade (CTCAE v. 4.0) | | |
| (CICAL V. 4.0) | | Second Occurrence: Hold drug for two weeks. If improved to ≤ grade 2 then restart cetuximab at dose level -1. If pruritus remains ≥ Grade 3 then discontinue cetuximab. |
| | | Third Occurrence: Hold drug for two weeks. If improved to ≤ grade 2 then restart cetuximab at dose level -2. If pruritus remains ≥ Grade 3 then discontinue cetuximab. |
| | | Fourth occurrence: discontinue cetuximab. |
| Rash, other (Grade per Table 5 below.) | | discontinue cetaximus. |
| ≥ Grade 3 | Maintain dose level | First Occurrence: Hold drug for two weeks. If improved to ≤ grade 2 then restart cetuximab at same dose level. If rash remains ≥ Grade 3 then discontinue cetuximab. |
| | | Second Occurrence: Hold drug for two weeks. If improved to ≤ grade 2 then restart cetuximab at dose level -1. If rash remains ≥ Grade 3 then discontinue cetuximab. |
| | | Third Occurrence: Hold drug for two weeks. If improved to ≤ grade 2 then restart cetuximab at dose level -2. If |

| Adverse Event NCI CTCAE Toxicity Grade (CTCAE v. 4.0) | Ficlatuzumab Dose | Cetuximab Dose | |
|---|---|---|--|
| | | rash remains ≥ Grade 3 then discontinue cetuximab. | |
| | | Fourth occurrence: discontinue cetuximab. | |
| Other, Grade ≥ 3 Events at least possibly related to ONLY ficlatuzumab | Hold drug until ≤ grade 1 or baseline, then reduce by one dose level. | Maintain dose level. | |
| Other, Grade ≥ 3 Events at least possibly related to ONLY cetuximab | Maintain dose level. | Hold drug until ≤ grade 1 or baseline, then reduce by one dose level. | |
| Other, Grade ≥ 3 Events at least possibly related to both ficlatuzumab and cetuximab | Hold drug until ≤ grade 1 or baseline, then reduce by one dose level. | Hold drug until ≤ grade 1 or baseline, then reduce by one dose level. | |
| Other, Grade ≥ 3 Events that are NOT related to or expected from either ficlatuzumab or cetuximab | If determined to be clinically significant, in the judgement of the treating investigator, hold until resolved to ≤ grade 1 or baseline and restart at same dose. | | |

- a. Sustained deficiency may require both chronic oral **and** IV replacement. An EKG is strongly recommended in the event of: 1) symptomatic Grade ≥ 3 hypomagnesemia or hypokalemia or 2) asymptomatic Grade 4 hypomagnesemia or hypokalemia. Interventions, including hospitalization as necessary for correction of electrolyte derangement, should occur in accordance with clinical severity and investigator judgment.
- b. "Intolerable" is to be determined by treating investigator opinion.
- C. Suggested steroid pulse of Prednisone 40 mg/daily for 5 days.

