8.3 Evaluations during study treatment

8.3.1 Every Two Weeks – Day 1 and Day 15 of each cycle (+/- 3 days)

Note: The following may be performed on the day of or within the 3 days prior to study drug administration. If the subject is deemed not acceptable for drug administration, refer to the visit delay and skipped visit description in Section 5.5. Subjects can return within the +3-day window, in 1 week, or for the next regularly scheduled treatment. If appropriate, the visit can be skipped and treatment can occur on schedule with the next regularly scheduled treatment (i.e., 2 weeks later).

- Physical examination, including vital signs, weight and ECOG performance status
- Adverse Event/Toxicity assessment with attribution
- Update of concomitant medications
- Complete blood count, including platelets and differential
- Blood chemistries:
 - o BUN, creatinine, electrolytes (K⁺, Na⁺, Cl⁻, CO₂), glucose, calcium, magnesium
 - Note: Refer to Table 4B regarding grading, repletion, holding treatment, and/or dose reductions.
- Liver function tests:
 - o total protein, albumin, total bilirubin, AST (SGOT), ALT (SGPT), and alkaline phosphatase
- Study drug administration
 - o For both agents: Recalculate the doses of both ficiatuzumab and cetuximab only if there is a ≥ 10% change in weight. Exception: If, in the opinion of the treating investigator, weight change of ≥ 10% is due to edema, recalculation of the ficiatuzumab dose is not required. This decision must be clearly documented.

8.3.2 Every 8 Weeks (the end of even cycles – "Day 28"/8 weeks, 16 weeks, etc.)

- Quality of life assessment (FACT-H&N) end of cycle 2 and cycle 6 only.
 - The FACT-H&N may be done cycle 3, day 1/cycle 7, day 1 for subjects who remain on treatment.
 - If a subject stops treatment per the cycle 2 or cycle 6 scan, the FACT-H&N scheduled for C2D28 or C6D28 can be done at the End of Treatment visit.

- Tumor measurements according to RECIST 1.1 may be done during the last week of an even cycle, by CT scan or MRI.
 - Tumor measurements must be performed every 8 weeks, +/- 7 days for (at least) the first 12 cycles. (See Section 8.3.3 regarding an optional tumor measurements schedule for subjects on treatment longer than 12 cycles.)
 - The schedule is independent of any treatment delays within the 2 cycles since the prior response assessment. (See Section 5.5.1 regarding missed and/or skipped visits.)

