15.3 Appendix C: Study Calendar (Also see Section 8)

| | Screening | - | Study Treatme | ent | | Falls | ما ا س |
|---|---|---------------------|----------------------|---|----------------------------------|--|---|
| | Within 28 | | 28 Day Cycles | ; 2 | | FOIIC | оw Up |
| | days of registration (except pregnancy within 14 days of registration) | Day 1 +/- 3 days | Day 15 +/- 3 days | Every 8 weeks ¹³ Day 28 +/- 7 days (C12+ Optional q12wks +/- 14d) | End Of Treatment ¹ | Non-PD Follow- up ³ q8wks +/- 2 week | PD Follow- up ¹⁹ q12wks +/- 2 weeks |
| Medical History | Х | | | | | | |
| Physical Exam & Vital Signs | Х | Х | Х | | Х | Z | |
| Height | Х | | | | | | |
| Weight | Х | X ⁴ | X ⁴ | | Х | Z | |
| ECOG Performance Status | Х | Х | Х | | Х | Z | |
| CBC with Differential ⁵ | Х | Х | Х | | Х | Z | |
| Serum chemistries and Liver function tests ⁵ | Х | Х | Х | | Х | Z | |
| Magnesium ⁵ | X | Х | Х | | Х | Z | |
| Documentation of Corrected Calcium | Х | | | | | | |
| Research (correlatives) blood | X 6 | | | X ⁷ | X | X 8 | |
| Pregnancy test | X 9 | | | | | | |
| Research biopsy ¹⁰ | Х | | | | | | |
| Confirmation of availability of archived diagnostic specimens | X 11 | | | | | | |
| Tumor measurements, RECIST 1.1 (CT or MRI) ¹² | Х | | | X ¹³ | X | Z | |
| FACT-H&N Symptom Index | X 6 | | | X ¹⁴ | X 14 | | |
| Tobacco Assessment | X 6 | | | | | | |
| Oropharyngeal & unknown primary cases, p16 Status 15 | Х | | | | | | |
| Registration/Randomization | Х | | | | | | |
| Cetuximab | | Х | Х | | | | |
| Ficlatuzumab | | X | Х | | | | |
| Concomitant medication review | Х | Х | Х | | Х | | |
| Adverse event evaluation | | Х | Х | | X ¹⁶ | X ¹⁷ | X 18 |
| Survival assessment | | | | | | Х | X ¹⁹ |

Page 71 of 76 v10, 05/23/2023

- ⁵ May be performed on the day of, or within the 3 days prior to study treatment.
- ⁶ May be performed during screening, or prior to drug administration on Cycle 1, Day 1.
- ⁷ For convenience, research blood may be drawn simultaneously with pre-treatment labs for the next cycle. *Subjects who transition to every-12-week tumor assessments will have the research blood drawn every 12 weeks, consistent with the tumor assessment schedule. Refer to Section 8.3.3*
- ⁸ Research blood will be obtained at the time of disease progression or censored for progression (see footnote 3 above, and Section 8.5.2) during the follow up period, then followed per the progressive disease follow up.

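### Table 4B acts on Grade 3 or higher hypophosphatemia, but no scheduled blood panel includes phosphate, so the rule has no systematic trigger

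*Combined protocol and SAP*

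**What the plan says.** The metabolic block of Table 4B (Section 5.5.6) covers "Hypomagnesemia, Hypokalemia, Hypophosphatemia, or Hyponatremia" as one group and gives the same text in the ficlatuzumab and cetuximab columns. For an asymptomatic Grade 3 or higher event the instruction is "Administer PO or IV replacement and reassess. If Grade ≤2, continue drug at same dose level"; if the event does not recover to that level, the drug is held. For a symptomatic event, recovery leads to a reduction of one dose level, and non-recovery leads to a hold.

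The text above the table sets two conditions. The guidelines apply to events as follows: "Adverse events observed and deemed to be at least possibly related to study drug(s) will be managed". Which drug is affected depends on attribution: "If the non-hematologic toxicity is at least possibly related to both ficlatuzumab and cetuximab, then both study drugs should be modified as described below". An event attributed solely to one drug affects that drug only.

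The chemistry list is the same in Sections 8.1 (screening), 8.3.1 (Day 1 and Day 15 of every cycle), 8.4 (end of treatment) and 8.5.2 (follow-up without progression). It covers urea nitrogen, creatinine, four electrolytes named in parentheses (potassium, sodium, chloride, CO2) and "glucose, calcium, magnesium". Under the Section 8.3.1 list, a note sends the site to Table 4B "regarding grading, repletion, holding treatment, and/or dose reductions". The Appendix C calendar has a row for "Serum chemistries and Liver function tests", a row for magnesium and a row documenting corrected calcium. It has none for phosphate.

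**The concern.** The panel that is meant to feed Table 4B cannot supply one of the table's four metabolic inputs. A site that follows the schedule exactly sees potassium, sodium and magnesium every two weeks and never sees phosphate.

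Two things are at stake. The first is detection. The asymptomatic row can only be reached by a measurement, and for this analyte none is scheduled. Screening does not include phosphate either, so a low value found on treatment may have no baseline for comparison. The second is reporting. Section 10.4.1 counts every patient from the first ficlatuzumab dose as evaluable for toxicity, and Section 10.6 tabulates toxicities with exact 95% intervals. For hypophosphatemia that denominator would include patients in whom nobody looked, and the count would depend on which sites happen to run phosphate locally.

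**Working it through.** The plan states no figure on this point. The check sets each metabolic trigger in Table 4B against every laboratory list in the protocol.

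| Analyte | 8.1 screening | 8.3.1 Day 1/Day 15 | 8.4 end of treatment | 8.5.2 follow-up (if performed) | Lists containing it |
|---|---|---|---|---|---|
| Magnesium | yes | yes | yes | yes | 4 of 4 |
| Potassium | yes | yes | yes | yes | 4 of 4 |
| Sodium | yes | yes | yes | yes | 4 of 4 |
| Phosphate | no | no | no | no | 0 of 4 |

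Could phosphate be read into one of these entries?

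- The word for electrolytes is followed by a closed parenthesis naming four analytes, and phosphate is not one of them.
- The liver panel includes alkaline phosphatase, which is an enzyme and gives no serum phosphate value.
- The chemistry row in Appendix C is generic, but the calendar refers to Section 8, where the contents are listed.
- Section 3.1 sets eligibility minima for magnesium, corrected calcium and potassium, and none for phosphate. This is weak evidence alone, because sodium has no minimum either.

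One of the four metabolic triggers therefore has no scheduled measurement, against two per 28-day cycle for each of the other three.

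Which branches of the rule does this affect?

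- Asymptomatic, Grade 3 or higher: needs a laboratory value and has no scheduled source. The action is replacement and reassessment, then a hold if there is no recovery. There is no dose reduction in this row.
- Symptomatic, Grade 3 or higher: can be reached if symptoms prompt an unscheduled test.

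For reporting, take an illustration with no cases recorded. The exact two-sided 95% upper limit for 0 of n is 1 − 0.025^(1/n).

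- n = 33, the planned eligible number per arm (Section 10.3): 1 − 0.025^(1/33) = 1 − 0.894 = 10.6%.
- n = 11, assuming that only one third of the arm ever had a phosphate result: 1 − 0.025^(1/11) = 1 − 0.715 = 28.5%.

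The one-third share is an assumption, because the documents do not say how many sites test phosphate. With no scheduled test, the number assessed could lie anywhere from 0 to 33. The tabulated interval would imply 33.

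**The case against.** The strongest reply is that the rule works on observed adverse events and is not limited to scheduled tests. Nothing bars an unscheduled or standard-of-care phosphate test, and Section 12.2 records any Grade 3 or higher event however it was found. That stands. A reader might infer that the rule cannot operate at all, or that phosphate is never measured; the documents support only that it is not scheduled. The reply is weaker for the asymptomatic row, since symptoms cannot prompt that test.

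A reader might also infer that the gap affects holding or reduction of both drugs in every patient. It does not. Action follows attribution, Arm A receives no cetuximab, and reduction belongs to the symptomatic row only.

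Nor should the follow-up list be counted as a required test that lacks phosphate: Section 8.5.2 collects those results only if they were obtained as standard of care.

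The importance can fairly be questioned. Hypophosphatemia is not in Table 1, Table 2, the phase Ib Grade 3 events in Section 1.4, or the categories of interest in Section 12.2. The nearest support is the unspecified electrolyte abnormalities that Section 1.7.1 lists with hypomagnesemia among the most common cetuximab events. So it cannot be said that a low reported rate would hide a real one, only that the rate could not be interpreted. The laboratory list is also the same in both arms, and the design is non-comparative.

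**Conclusion.** The inconsistency is real and narrow. Table 4B names a laboratory trigger that appears in 0 of 4 chemistry lists and in no calendar row, while the panel that omits it points to that table. The rule can still be set off by an unscheduled or local test, but it has no systematic trigger, least of all in the asymptomatic row, and the reported hypophosphatemia rate would reflect local testing practice to an unknown degree.

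The clinical size cannot be stated, because the documents give no event rate. PFS, sample size, power and the futility rule are unaffected. The conclusion rests on reading the lists in Section 8 as complete. It would fall if the generic chemistry row in Appendix C were shown to include phosphate at every site, which no text says.

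**What to change.** Reconcile Table 4B with the laboratory lists in Sections 8.1, 8.3.1, 8.4 and 8.5.2 and with Appendix C, so that every laboratory trigger in the table has a matching scheduled test. Phosphate could be run on blood already drawn, at the cost of one more analyte per panel and with no extra visit or venipuncture. Which passage changes is for the sponsor to decide.

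Sections 5.1 and 5.4.1 end ficlatuzumab dosing by March 31, 2021, and this version is dated May 23, 2023, so a changed panel cannot help patients already treated. For them the remedy lies in the report: give the number of patients per arm with any phosphate result, show it beside the hypophosphatemia count, and state that phosphate was not a scheduled test. The tested patients may be a selected group, so a percentage based on them needs the same caution. The cost is a count from local laboratory records and a sentence in the safety section.

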5.5.8 Cetuximab Infusion Reaction

A cetuximab infusion reaction will be managed as described in Table 6 below. If there is any question as to whether an observed reaction is an infusion reaction of Grades 1-4, [name] should be contacted immediately to discuss and grade the reaction.

Should an infusion reaction occur, retreatment will be managed as follows: Once a cetuximab infusion rate has been decreased due to an infusion reaction, it will remain decreased for all subsequent infusions. If the subject has a second infusion reaction with the slower infusion rate, the infusion should be stopped, and the subject should receive no further cetuximab treatment. If a subject that experienced an initial cetuximab infusion reaction experiences a Grade 3 or 4 infusion reaction at any time, the subject should receive no further cetuximab treatment.

Table 6: Management of Cetuximab Infusion Reaction

| Grade | Management |
|--|--|
| Grade 1: Transient flushing or rash; drug fever < 38° C (< 100.4° F) | For mild infusion reactions manifesting only as delayed drug fever, consider administering prophylactic antihistamine medications for subsequent doses. Maintain the cetuximab dose but slow the infusion rate by 50%. Acetaminophen or a non-steroidal anti-inflammatory drug (NSAID) may be administered prior to subsequent cetuximab infusions, if not otherwise contraindicated in subjects. |
| Grade 2: Rash; flushing; urticaria; dyspnea; drug fever ≥ 38° C (≥ 100.4° F) | For moderate infusion reactions manifesting only as delayed drug fever, slow the infusion rate for cetuximab by 50%, and consider administration of antihistamine medications and/or steroidal medications. Maintain the cetuximab dose. Acetaminophen or a non-steroidal anti-inflammatory drug (NSAID) may be administered prior to subsequent cetuximab infusions, if not otherwise contraindicated in subjects. |
| Grade 3: Symptomatic bronchospasm with or without urticaria; parenteral medication(s) indicated; allergy- related edema/angioedema; hypotension | Severe infusion reactions requires immediate interruption of cetuximab infusion and permanent discontinuation from further treatment with cetuximab. Appropriate medical therapy including epinephrine, corticosteroids, diphenhydramine, bronchodilators, and oxygen should be available for use in the treatment of such reactions. Subjects should be carefully observed until the complete resolution of all signs and symptoms. |

| Grade 4: | NO FURTHER CETUXIMAB |

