|-------------|---|
| Anaphylaxis | Life-threatening infusion reactions require immediate interruption of cetuximab infusion and permanent discontinuation from further treatment with cetuximab. Appropriate medical therapy including |
| | epinephrine, corticosteroids, diphenhydramine, bronchodilators, and oxygen should be available for use in the treatment of such reactions. Subjects should be carefully observed until the complete resolution of all signs and symptoms. |

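### Ficlatuzumab has no infusion-reaction or anaphylaxis rule, so Table 4B's written default after a Grade 3-4 reaction is to re-dose one level lower

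*Combined protocol and SAP*

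**What the plan says.** The only infusion-reaction rule in the treatment plan is Section 5.5.8, and its scope is one drug: "A cetuximab infusion reaction will be managed as described in" Table 6. For Grade 3, Table 6 says "Severe infusion reactions requires immediate interruption of cetuximab infusion and permanent discontinuation from further treatment with cetuximab". For Grade 4 (anaphylaxis) it says "Life-threatening infusion reactions require immediate interruption of cetuximab infusion and permanent discontinuation from further treatment with cetuximab". Neither entry mentions ficlatuzumab.

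Section 5.5.6 covers non-hematologic toxicity from either drug, which "will be managed according to the guidelines for dose interruption, delay, or reduction". Those are set out in Table 4B, where no row names infusion reaction, hypersensitivity or anaphylaxis. The residual rows at the end of the table take other events of Grade 3 or higher. For "Events at least possibly related to ONLY ficlatuzumab", the ficlatuzumab instruction is "Hold drug until ≤ grade 1 or baseline, then reduce by one dose level". The row for "Events at least possibly related to both ficlatuzumab and cetuximab" gives the same instruction for each drug. Neither row has an upper grade limit.

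Ficlatuzumab starts at 20 mg/kg every 2 weeks (5.1.2). Table 3 sets the reduced levels at 15 and 10 mg/kg.

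**The concern.** Ficlatuzumab and cetuximab are both IgG1 monoclonal antibodies given by infusion. The plan stops one permanently after a severe or life-threatening reaction and, by default, re-doses the other. Arm A patients receive no cetuximab, so Table 6 can never apply to them.

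The default also sits badly with the entry criteria. Section 3.2 excludes patients with a past severe allergic or anaphylactic reaction to recombinant proteins or to excipients of the study drug, and those with a past severe infusion reaction to cetuximab or another monoclonal antibody. A reaction of that kind before entry bars a patient. The same reaction to ficlatuzumab on study leads, as the table is written, to another infusion. The stake is the safety of an individual patient; no endpoint, sample size or analysis is affected.

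**Working it through.** **Step 1: which written stops would a ficlatuzumab reaction meet?** Take a Grade 3-4 reaction at 20 or 15 mg/kg that clears before the next 2-weekly dose.

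| Section | What triggers a permanent stop | Reached? |
|---|---|---|
| 5.5.2 | Attributable Grade 3-4 toxicity at 10 mg/kg (may resume if there is clinical benefit) | No, the dose is above 10 mg/kg |
| 5.5.3 | Two consecutive missed doses from ficlatuzumab toxicity (may resume if there is clinical benefit) | No, it resolves too soon |
| 5.5.4 | Confirmed interstitial lung disease; other acute pulmonary symptoms allow retreatment at Grade 1 | No, even if bronchospasm triggers the interruption |
| 5.5.6, Table 4B, hepatic | AST or ALT above 3x ULN with bilirubin above 2x ULN | No |
| 5.5.8, Table 6 | Grade 3-4 cetuximab infusion reaction | No, cetuximab only |

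What remains is the residual row: hold, then one level lower. That is 20 to 15 mg/kg, or 15 to 10 mg/kg. The interstitial lung disease and hepatic rules show that the protocol does write event-specific permanent stops for ficlatuzumab elsewhere.

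**Step 2: how often might it arise?** The protocol gives no reaction rate for ficlatuzumab. None appears among the dose-limiting toxicities (DLTs) or listed related SAEs in 1.6.3, in Table 1, or among the phase Ib Grade 3 events in 1.4. Section 1.6.3 also reports no post-treatment anti-drug antibodies.

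- Patients with DLT information: P05538, 24 + 13 + 4 = 41; P05670, 19; P06162 phase 1b at the recommended dose, 12; phase Ib in head and neck cancer, 12. Total 41 + 19 + 12 + 12 = 84.
- One-sided 95% upper limit for 0/84: 1 - 0.05^(1/84) = 0.0350. Over the 74 patients planned in 10.3: 0.0350 x 74 = 2.6. Over 37 in Arm A (74/2): 1.3.
- Related SAEs, P05538 and P05670 only: 41 + 19 = 60. For 0/60: 1 - 0.05^(1/60) = 0.0487, and 0.0487 x 74 = 3.6.

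The lower end of each range is zero. The first limit assumes that all 84 patients were assessed for DLTs and that a Grade 3-4 reaction would have counted as one. The second assumes that a severe reaction would have been reported as a related SAE and that the listing in 1.6.3 is complete.

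**The case against.** The strongest reply is that nobody has to re-dose. Section 5.4.1 ends treatment for an unacceptable adverse event or on the investigator's judgement, and 5.5.6 calls its rules guidelines. Under 12.3, SAEs in either arm go to the sponsor and the data and safety monitoring board within 24 hours, whatever the attribution. A life-threatening reaction is an SAE by definition (12.1), so the sponsor would normally know well before the next dose. All of this stands, and it makes re-exposure a default and not a certainty. But 5.4.1 leaves the decision open, and 12.3 is a reporting duty that says nothing about dosing. The contact route in 5.5.8, under which a named person "should be contacted immediately to discuss and grade the reaction", sits in the cetuximab section.

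The Investigator Brochure and Pharmacy Manual may also contain reaction guidance. That cannot be checked here. Section 7.1.1 cites the manual for preparation and administration, and Section 5.5 sends the reader to neither document for reactions. The entry exclusions and the required prior cetuximab exposure also select for antibody tolerance, so the limits above may overstate the risk in this population.

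Three stronger readings are tempting and not supported:

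- *Table 6 and the residual rows conflict for cetuximab.* They do not. Section 5.5.8 is the specific, mandatory rule, and a residual row naturally covers events that have no rule of their own.
- *A patient must be re-exposed twice before any written stop applies.* Section 5.4.1 is a written stop, available after the first reaction.
- *The infusion cannot be slowed.* Section 5.1.2 allows 30 to 60 minutes, so a site can move from 30 to 60 minutes and halve the rate. Slowing is permitted, though not required.

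**Conclusion.** The gap is real and minor. For a Grade 3-4 infusion reaction or anaphylaxis attributed to ficlatuzumab above 10 mg/kg, the only event-level instruction in Section 5.5 is to hold and re-dose one level lower. That is inconsistent with the protocol's own handling of cetuximab reactions and with its entry exclusions. What stands against it is discretion and reporting, not a dosing rule.

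The number affected may well be zero. The upper limits of 2.6 and 3.6 of 74 patients show only that the earlier data cannot exclude a rate of a few percent; they are not forecasts. The documents give no rate from which to project the chance of a reaction in this trial. Ficlatuzumab dosing ended by March 31, 2021 (5.1, 5.4.1), before this version (v10, 05/23/2023), so no patient now on treatment would benefit. The value of a correction lies mainly in not carrying the table forward, for example into the phase III step foreseen in 10.3.

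**What to change.** Add a row to Table 4B: for a Grade 3-4 infusion reaction or anaphylaxis at least possibly related to ficlatuzumab, permanently discontinue ficlatuzumab. State that this row is exempt from the options in 5.5.2 and 5.5.3 to resume when there is clinical benefit.

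Add one exception for Arm B, where ficlatuzumab follows cetuximab by 30 to 60 minutes (5.1.3) and the responsible drug may be unclear. When attribution between the two is uncertain, stop cetuximab under Table 6 and decide on ficlatuzumab with the Sponsor-Investigator before any further dose. This preserves the 5.5.2 option to continue ficlatuzumab after a cetuximab toxicity.

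The cost is one table row and two sentences, with no change to visits, sample size or analysis. The downside is that a few patients could lose a drug they might have tolerated on rechallenge, in a population for whom 1.1 says no standard therapy exists.
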